This is a 24-week, two-arm, multicenter feasibility parallel randomized controlled trial designed to evaluate the usability and effectiveness of LuCApp to improve self-management of symptoms and quality of life in lung cancer patients. The protocol has been developed in accordance with the CONSORT-EHEALTH checklist (16). The flow diagram for recruitment and randomization is shown in Figure 1.

Figure 1 - Flow diagram for recruitment, randomization and data collection

Participants

Adults of both sexes with lung cancer (small and non-small cell) will be assessed for eligibility at participating sites. Study inclusion criteria will be (

Table 1):

- over 18 years of age individuals of both sexes;
- diagnosed with small or non-small cell lung cancer;
- patients eligible for chemotherapy, immunotherapy or biological therapy;
- patients diagnosed with non-resectable tumor and eligible for neoadjuvant therapies;
- life expectancy of six months or more;
- a performance status between 0 (asymptomatic) and 2 (symptomatic, <50% in bed during the day) according to the Eastern Cooperative Oncology Group (ECOG) score;
- patients fluently speaking Italian;
- patients able to provide informed consent to participate in the study;
- patients who own a smartphone that can access either the iOS or the Android platform.

Although internet literacy was not defined as an explicit eligibility criterion in this study, it works as a *de facto* selection criterion since only individuals that personally own a smartphone can be enrolled in the study. It was assumed that, if individuals owned a smartphone, they would be able to use it.

Patients will be excluded if they: i) are unable to provide written informed consent, ii) are unable to use the app and all other materials (i.e. blind), iii) have received, are receiving or plan to receive radiotherapy or surgical resection as their management will likely be different from patients undergoing pharmacological therapy. Furthermore, patients that are already included or about to join other clinical trials and individuals who are already using another smartphone application to self-manage cancer will not be considered eligible for the trial.

Table 1 - Summary of inclusion and exclusion criteria

Inclusion criteria	Exclusion criteria

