Symptoms are subjective experiences self-reported by the patient, and are a subset of patient perceptions of health status and HRQoL (21). HRQoL is a multidimensional construct of diverse functional scales (e.g. physical function, psychological function, social role function) and symptom scales (e.g. disease-related or treatment-related symptoms) (21).

Three questionnaires were selected and are described in the next paragraphs.

a) EQ-5D-5L

The EQ-5D-5L is a generic preference-based measure of health status, which is the most commonly used tool used to derive utility values that can be utilized within an economic evaluation model (22). This tool is also commonly used in lung cancer trials (23). It includes questions covering five domains: mobility, self-care, usual activities, pain and discomfort, and anxiety and depression. For each domain, 5-level questions are posed. Additionally, patients are asked to fill in how they feel today on a vertical visual analogue scale (VAS). Validated versions are available for paper-based and via smartphones and tablet administration.

The questionnaire will be administered at baseline, every 3 ± 1 weeks to take into account that visit intervals may vary between patients and across therapies (in this way the completion of the questionnaire will happen approximately 1 day before each cycle of treatment for chemotherapy patients), and at the end of the study period. This frequency of administration is in line with other trials involving lung cancer patients that administered the EQ-5D (24, 25).

b) FACT-L (lung cancer module):

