The Functional Assessment of Cancer Therapy-Lung (FACT-L) questionnaire is a disease-specific measure capturing multidimensional aspects of lung cancer patients' quality of lives (26). The symptoms covered are shortness of breath, weight loss, consciousness, cough, hair loss, appetite, tightness in chest, breathing. FACT-L is the result of the combination of FACT-G (general module and core instrument), which is a general quality of life questionnaire for use in a variety of chronic illness conditions, with a Lung Cancer subscale. It is validated in the Italian version. These questionnaires are extensively used in clinical research, health care delivery studies, symptom management studies, psychological intervention studies, and other treatment evaluations. Studied in various subgroups of lung cancer patients receiving different courses of treatment. The administration mode could be interviews (in-person or telephone), self-administration (in the clinic or by mail) or computer administered questionnaire. Available data suggest that while there are small differences in the way people respond based on mode of administration, these alternate formats are essentially

equivalent, particularly when reporting data at the group level (27). The questionnaire will be administered at baseline, at 12 weeks, and at the end of the study period.

c) Hospital Anxiety and Depression scale (HADS)

HADS is a self-assessment scale developed to detect states of depression, anxiety and emotional distress amongst patients treated for a variety of problems in the setting of out-patient clinics (28). It is composed of two 7-item scales for depression and anxiety respectively. All symptoms relating to physical disorders (e.g. dizziness, headaches) were excluded to avoid interference with other diagnoses (29). HADS was identified as one of the most commonly used PROMs in advanced-staged lung cancer clinical trials of pharmaceutical agents (30), and has been used to measure HRQoL in NSCLC patients (31).

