The Italian version of the HADS showed to be valid and reliable, similarly to those results obtained in other languages (32). Specifically, there was a high internal consistency of both anxiety and depression scales. Factor analysis confirmed the bi-dimensionality of the HADS model. Results showed that the two scales are not sufficient to detect distinct cases of anxiety and depression, which is supported by other studies. This is likely because patients with one or the other disorder are likely to have a common area of emotional disturbance, which is not differentiated by the HADS. The use of the total scale has shown high internal consistency. HADS has been used in various clinical settings, in cross-section and longitudinal studies as an outcome measure. Results show that the scales and total scale are sensitive to change, but may be less likely to the smaller changes.

Another study conducted an updated literature review to assesses the validity of HADS (29). They highlight that HADS is administrated mainly in patients with cancer or other somatic illnesses. They looked at the number of factors in HADS identified by factor analysis, the correlation between the subscales of HADS, and the internal consistency of the subscales (Cronbach's alpha). They confirm the two-dimensionality of the model, as well as the fact that although depression and anxiety are very different, it is difficult to distinguish these constructs empirically. The reliability of this self-report instrument was confirmed in all translations (based on Cronbach's alpha). Results also show that the HADS is a good tool to identify patient with emotional disorders. Its concurrent validity with other scales ranged between good and very good. The

questionnaire will be administered at baseline, at 12 weeks, and at the end of the study period.

(2) Cancer supportive care needs

LuCApp is to be used in the context of cancer supportive care. Given its functionalities in terms of monitoring and providing support and information, it may be that some of the unmet needs of cancer patients surrounding their supportive care may be met. Lung cancer patients have greater unmet supportive care needs than other cancer patients (33).

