The supportive care needs survey, short form (SCNS-SF34) is a needs assessment questionnaire in cancer supportive care measuring the gap between patients' experience and their expectations (34, 35). It consists of 31 items covering four domains: psychological needs, health system and information needs, physical and daily living needs, and patient care and support needs. For each question, patients are asked to provide an indication of their level of need on a 5-point Likert scale (1: not applicable; 2: satisfied; 3: low need; 4: moderate need; 5: high need) (36). It is applicable to research, clinical settings (36) and routine care (37). It is commonly used to identify priorities for action, to assess the adequacy of current practice in order to identify areas for improvement, and as an intervention tool to reduce patients' perceived needs.

The SCNS-SF34 has been translated and culturally validated (38), and more recently validated in a multicenter study led by [name]. Its construct validity and internal reliability have been demonstrated (36). Its administration as pen-and-paper has been successfully psychometrically tested. It has also been adapted for electronic administration (via touchscreen computer), where the data collected was shown to be equivalent to the data collected from the pen-and-paper version (39).

The SCNS-SF34 will be administered at the end of study, to assess whether some of the supportive care needs were fulfilled in the different study arms. There is still not evidence that the SCNC-SF34 is responsive to change over time, however this is currently being tested in an ongoing longitudinal study assessing how perceived needs change over time over the course of the cancer journey (newly diagnosed cancer patients are being administered the survey four times over the first five years after diagnosis) (36).

(3) Burden on caregivers

The Zarit Burden Interview (ZBI) is a 22-item self-administered scale measuring caregiver burden in health, psychological well-being, finances, social life, and relationship with patient. Each item is measured on a 5-point Likert scale (0=never to 4=nearly always). The total burden is obtained by adding the scores across all 22 items: the higher the score, the higher the burden. Shorter versions have been developed with 18 and 12 items.

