The ZBI was selected on the basis that it has been used in cancer patients (40) and is one of the most widely referenced scales in studies measuring caregiver burden (41). The ZBI was developed for nervous system disorders and mental disorders, but has also been applied to cancer patients (42-45). In one study, the authors explore if caregiver burden was in agreement with patient ratings. Patients had different forms of advanced cancer and their carer's Zarit scores were relatively low. They conclude that Zarit may not capture some important aspects of burden in cancer, given that it was initially developed for dementia patients (42). A second study used the ZBI to assess the impact of breathlessness in lung cancer patients on their caregivers, and found high levels of unmet needs and burden particularly in the more severe cases (43).

Assessment timing of the ZBI will be at the end of the study, and will be administered in paper format. Its criterion validity, construct validity and internal consistency have been demonstrated (40). The Italian version of the questionnaire is valid, reliable and useful for use in clinical contexts and in future studies (46).

(4) Usability and satisfaction of LuCApp

At the end of the study, patients in the intervention arm will have an opportunity to provide feedback on strengths and shortcomings of the application, including unintended/unexpected effects. This session will be of interest also for those who did not use the application as intended by the developers. Use and adoption metrics are important process outcomes to understand the mechanism of action of such intervention. The mHealth application contains a tracking system. Frequency and duration of logins and the activity will be recorded and evaluated. To test user satisfaction with the App, a modified computer system usability questionnaire (CSUQ) will be utilized at the end of the study and will be administered to both patients and clinicians using LuCApp. The CSUQ is an overall satisfaction questionnaire that was developed together with other subjective usability measures at IBM in the nineties (47). The CSUQ is identical to the Post-Study System Usability Questionnaire (PSSUQ),

[figure not shown]

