except that the wording of the items does not refer to a usability-testing situation but is rather appropriate for a field-testing situation. The CSUQ was later adapted for mobile apps usability testing to elicit participant satisfaction with the PAediatric Risk Assessment (PARA) app, a mHealth tool developed to help health care professionals in resource-limited settings detect patients at high risk of both in-hospital and post-discharge mortality (48). Based on this revised version, the questionnaire was further elaborated upon: the final version consists of 12 items evaluated on a Likert scale ranging from 1 (“Strongly agree”) to 7 (“Strongly Disagree”). In addition, three qualitative questions were added to draw further information on the application and on the generalizability of LuCApp in the current and other clinical contexts: 1) “What do you like the most about the App?”; 2) “What do you like the least about the App”; 3) “How could the App be changed to make it easier to use?”. No validated Italian version of the CSUQ was available, so the authors, in cooperation with healthcare professionals of the participating sites, developed the current version. The questionnaire will be administered at the end of the study.

(5) Resource use

The perspective taken for the evaluation of resource consumption will be that of the National Healthcare System. In order not to overload patients and the App design with additional modules, resource use will be captured through patients reports of symptoms and clinicians actions in response to those symptoms (e.g. prescriptions, hospitalization, change in therapy). Moreover, additional information will be obtained for both control and treatment group patients via a form administered by the physician during the clinics. Unitary costs will be expressed as euros 2018. Drug unitary costs will be derived from national price listings, laboratory and instrumental tests will be valued according to the outpatient procedures formulary in accordance with the ongoing policies of Lombardy Region as well as eventual hospitalizations.

Figure 6 summarizes the data collection process throughout the study.

Figure 6 - Time-points of outcomes assessment

Sample size

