Assuming a constant recruitment rate of 6 patients per week (2 patients per centre) the study is planned to recruit consecutively for 26 weeks (Figure 9).

Figure 9 - Planned recruitment process

Randomization

Randomization services will be provided by AdvicePharma via a computer system using randomly permuted blocks and stratified by trial centers and therapy (i.e.

chemotherapy, immunotherapy and biological therapy). Nurses or physicians involved in the study will take care of the enrollment phase. After signature of informed consent, a randomization code will be generated electronically and assigned to the patient. During the informed consent procedure, the team will go carefully through the different aspects of the study design and will present LuCApp as well as the usual care alternative. During this phase the patient will have an opportunity to discuss her level of experience with mobile technology.

The study is nonblinded, in fact it is not possible to blind the participants when this type of intervention and these outcomes are under investigation.

Participants will remain on study until discontinuation of cancer treatment, voluntary withdrawal, study termination or death.

Statistical methods

The baseline differences between the intervention and control groups will be assessed using the chi-square (χ^2) test for binary demographic data and the independent sample t-test for continuous variables. We will summarize graphically and numerically the distributions of symptoms, outcomes as well as covariates.

For the primary quality of life endpoint, two groups t-test will be used to compare changes from baseline in FACT-L in the experimental group and the control group 12 weeks after randomization. A multivariable linear regression model, with change score as the dependent variable, adjusted for covariates will be fitted. The proportion of patients in each arm who experienced improved, unchanged, or worsened scores from baseline will be compared using χ^2 or Fisher's exact test. This analysis will be run for both any change and clinically meaningful changes for specific subscales (51). The analyses will be repeated at 24 weeks after randomization.

For all other questionnaires, changes from baseline in the LuCApp group and the control group at 12 and 24 weeks after randomization will be computed using t-test comparison. The SCNS-SF34, usability and ZBI data results will be summarized graphically and numerically.

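### Study participation ends when cancer treatment stops, but FACT-L, HADS, the QALYs and the 6-month death rule need data after that point

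*Combined protocol and SAP*

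**What the plan says.** The end-of-participation rule stands at the close of the Randomization section: "Participants will remain on study until discontinuation of cancer treatment, voluntary withdrawal, study termination or death". Stopping treatment sits beside withdrawal and death as an exit, in both arms. The plan does not say whether completing a planned course, or changing therapy, counts.

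Other sections set outcomes on a calendar:

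- Trial design: "This is a 24-week, two-arm, multicenter feasibility parallel randomized controlled trial".
- FACT-L: "The questionnaire will be administered at baseline, at 12 weeks, and at the end of the study period". The Sample size section gives the last time as 24 weeks and makes the 12-week TOI change primary.
- HADS: the "questionnaire will be administered at baseline, at 12 weeks, and at the end of the study period".
- Statistical methods: FACT-L is compared 12 weeks after randomisation and again at 24; the other questionnaires are compared at 12 and 24 weeks. A death before 6 months is scored zero on EQ-5D. Survival runs from enrolment, with living patients censored when last followed. QALYs combine EQ-5D utilities with survival in both arms.

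The remaining instruments are timed more loosely. For EQ-5D, "The questionnaire will be administered at baseline, every 3 ± 1 weeks to take into account that visit intervals may vary between patients", with rounds falling just before each chemotherapy cycle, plus a round at the end of the study period. "The SCNS-SF34 will be administered at the end of study"; "Assessment timing of the ZBI will be at the end of the study"; the usability questionnaire is also due at end of study. None of these three has a stated week.

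**The concern.** A patient who stops treatment at week 8 and then leaves the study has a baseline TOI and nothing after it. A patient who stops at week 10 and dies at week 20 may never be recorded as dead, so the zero rule cannot be applied and the QALY rests on incomplete survival.

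Stopping happens after randomisation and is plausibly linked to toxicity, progression or decline. It could also differ by arm, because the permitted clinician responses to app alerts include dose modification. The planned t-tests would then compare those who stayed on treatment rather than all those randomised. The direction of any imbalance is unknown.

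**Working it through.** **Inputs from the documents (Sample size).** TOI difference 6, SD 11.54, 120 evaluable, 30% attrition, 156 enrolled, so 78 per arm. Every other input below is an assumption.

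**1. The plan's own figure.** n per arm = 2(1.960 + 0.842)² × 11.54² / 6² = 58.1, so 59 by the normal formula. The t-test solution is 59.05, so 60 per arm and 120 in total. Then 120 × 1.3 = 156. The plan's figures reproduce, and this point rests on no error in them.

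**2. The exit rule against each outcome.**

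| Outcome | Timing in the plan | Against the exit rule |
|---|---|---|
| FACT-L/TOI, HADS | 12 and 24 weeks after randomisation | Conflict |
| EQ-5D zero rule, QALYs | Deaths to 6 months; both arms | Conflict |
| Survival | Enrolment to death, or censored when last followed | Workable, but censoring may be informative |
| Interim EQ-5D | Follows visits and cycles | Ambiguous |
| SCNS-SF34, ZBI, usability | End of study, no week | Ambiguous; an exit questionnaire is a possible reading |

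**3. Exposure** (constant weekly stopping rate r, deaths ignored). The share off study by week T is 1 − exp(−rT). For r = 0.01, 0.02, 0.03 this is 11%, 21%, 30% by week 12 and 21%, 38%, 51% by week 24.

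**4. TOI bias with no true effect.** Let leavers be s points worse than stayers, with loss pL (LuCApp) and pC (control), and each arm's all-randomised mean change zero. Stayers in an arm then average s·p.

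- Complete cases: bias = s(pL − pC).
- Last observation carried forward (leavers scored zero change): bias = s[pL(1 − pL) − pC(1 − pC)].

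| Loss, LuCApp v control (s = 10) | Complete-case bias | False positives | LOCF bias |
|---|---|---|---|
| 20% v 20% | 0.0 | 5.1% | 0.0 |
| 17.5% v 12.5% | 10 × 0.05 = 0.5 | 5.7% | 10(0.1444 − 0.1094) = 0.35 |
| 25% v 15% | 10 × 0.10 = 1.0 | 7.7% | 10(0.1875 − 0.1275) = 0.60 |
| 30% v 20% | 10 × 0.10 = 1.0 | 7.3% | 10(0.21 − 0.16) = 0.50 |

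False-positive rates are from 20,000 simulated trials of 78 per arm. With s = 5 the complete-case bias is 5 × 0.05 = 0.25 to 5 × 0.10 = 0.5. A missing-at-random analysis on baseline TOI (correlation 0.6 assumed, s = 10) leaves 0.5, 1.0 and 1.0 points and about 6 to 8% false positives, because baseline does not explain why these patients left. Signs reverse if control loses more.

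**5. Effect of continued follow-up.** Suppose 83% of those who stopped by week 12 are alive (r = 0.02, weekly death hazard 0.005 on treatment and 0.03 after) and 80% of them respond: q = 0.83 × 0.80 = 0.664. Arm bias = s·p − s·p·q/(1 − p + p·q). For 25% v 15% this is 0.69 − 0.45 = 0.24. The three unequal cases give 0.13, 0.24 and 0.21 points, with false positives of 5.0 to 5.2%.

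**6. Survival if vital status also stops at exit** (r = 0.02, hazard 0.005 on treatment). The censored Kaplan-Meier estimate at 24 weeks is exp(−0.005 × 24) = 88.7%. True survival is exp(−0.025 × 24) + ∫₀²⁴ 0.02·exp(−0.025t)·exp(−h(24 − t))dt. For post-stopping hazard h = 0.005, 0.01, 0.02, 0.03 it is 88.7%, 86.6%, 82.9%, 79.7%. At h = 0.03, 78 × 0.203 = 15.8 deaths occur per arm and 78 × (0.005/0.025)(1 − exp(−0.6)) = 7.0 are seen. The log-rank false-positive rate is 4.8% if stopping is equal, and 6.8% if one arm stops a mean 3 weeks later after risk rises.

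**7. 24 weeks against 6 months** (taken as 26 weeks, h = 0.03). Deaths in the gap across 156 patients:

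- r = 0.01: 108.8 on treatment × 0.005 × 2 + 21.9 off treatment × 0.03 × 2 = 2.4.
- r = 0.03: 67.3 × 0.005 × 2 + 51.5 × 0.03 × 2 = 3.8.

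**The case against.** The best defence is that the rule is deliberate. LuCApp targets the side effects of therapy and its tips follow the patient's current therapy, so an on-treatment question is coherent. That is a legitimate choice, but the plan never states it, and analyses at fixed weeks after randomisation, survival from enrolment and QALYs in both arms answer a different question.

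A second defence is that the rule meant something narrower. The 6-month death rule does suggest that vital status was to be followed, and Figures 1 and 6 and the consent pages are not visible. This stands as a reason to reconcile the text; sites will still work from the written sentence. If planned completion counts as stopping, stratifying by therapy should help balance it, and such exits need not be informative.

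Third, the plan has a missing-data assessment, several imputations and mixed models, and calls itself a pilot. These soften the problem. They do not cure it: an early leaver supplies only a baseline TOI, and standard multiple imputation and mixed models assume missing at random. The pilot still plans a powered TOI comparison.

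Two stronger readings are tempting. A reader might infer that the rule contradicts every outcome; the table above shows that it does not. A reader might also infer that the primary comparison is biased or short of patients because of this rule. The documents do not support that: they give no stopping rate and no sign of imbalance, only patients who stop before week 12 affect the primary, and the 30% allowance may already include some of them. That allowance protects numbers, not comparability.

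**Conclusion.** The point holds as a conflict in the text with a possible, unproven bias. It is firm for FACT-L/TOI, HADS, the zero rule and the QALYs; for survival the issue is informative censoring; for interim EQ-5D and the end-of-study instruments it is ambiguity. The TOI effect is modest even under unfavourable assumptions and vanishes when the arms lose patients equally and with equal shortfall. Week 24, survival and QALYs carry more of the risk, because more patients will have stopped by then and later deaths may go unseen. These sizes depend on assumed stopping rates, shortfalls and hazards. The log-rank example in particular needs a six-fold rise in hazard plus an arm difference in stopping time. The change should be made because it is small and removes most of the exposure, not because harm has been shown.

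**What to change.** Reconcile the Randomization sentence with Sample size and Statistical methods. This concerns data collection only, not treatment.

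- State that stopping cancer treatment does not end data collection, and define stopping: whether planned completion or a change of therapy counts.
- For all randomised patients who have not withdrawn consent, collect FACT-L and HADS at 12 and 24 weeks, EQ-5D at least at 12 and 24 weeks (timed from randomisation once cycles cease), and SCNS-SF34, ZBI and, for LuCApp patients, the usability questionnaire at end of study. If EQ-5D is reduced, say that QALYs for those patients rest on fewer points.
- Record vital status to the 6-month point, or align the zero rule to 24 weeks.
- Extend home paper and telephone collection, now described only for usual care, to LuCApp patients who no longer use the app.
- State whether app use and alerts continue after stopping. This review prescribes neither.
- Resource use partly depends on clinic contact ("additional information will be obtained for both control and treatment group patients via a form administered by the physician during the clinics"). Say whether that form continues; if not, report later resource use as incomplete.
- Report number, timing and reason for stopping, by arm.
- If an on-treatment question was intended, state it and describe the 24-week, survival and QALY results accordingly.

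Cost: sample size and trial length are unchanged. The documents give no costs, so calling this cheap is a judgement. Under the assumed hazards, 14 to 38 living stoppers need contact at week 12 and 22 to 52 at week 24. Keeping the full EQ-5D schedule would add about 116 to 297 of 156 × 8 = 1,248 rounds. Downsides are extra calls, some burden on sicker patients, a check that consent covers the follow-up, and some data still missing through death and non-response.
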